### 6.2.7 Contraception

Women of non-childbearing potential are defined as permanently sterile (ie, due to hysterectomy, bilateral salpingectomy, bilateral oophorectomy) or postmenopausal (defined as at least 12 months post-cessation of menses without an alternative medical cause). Women who are of non-childbearing potential will not be required to use contraception.

Female patients of childbearing potential must be established on ( $\geq 3$  months prior to Screening) and agree to continue to use the same highly effective methods of birth control (ie, contraceptive measure with a failure rate of  $< 1\%$  per year) in conjunction with male barrier contraception (ie, male condom with spermicide) throughout the study and for 9 weeks after the administration of the last dose of study drug. Highly effective methods of contraception include:

- Intrauterine device (IUD; Mirena®)
- Established use of oral (PO), implanted, transdermal, or hormonal method of contraception associated with inhibition of ovulation
- Bilateral tubal ligation
- Permanent birth control via the Essure procedure

Male patients will be surgically sterile for at least 90 days or when sexually active with female partners of childbearing potential will be required to use a male condom with spermicide (if locally approved for use) throughout the study and for 9 weeks after the last dose of study drug.

Patients who practice true abstinence, because of the patient's lifestyle choice (ie, the patient should not become abstinent just for the purpose of study participation) are exempt from contraceptive requirements. Periodic abstinence (eg, calendar, ovulation, symptothermal, postovulation methods) and withdrawal are not acceptable methods of contraception. If a patient

who is abstinent at the time of signing the ICF becomes sexually active they must agree to use contraception as described above.

For male patients, sexual intercourse with female partners who are pregnant or breastfeeding should be avoided unless condoms are used from the time of administration of the first dose until 9 weeks after administration of the last dose of study drug. Male patients are required to refrain from donation of sperm from Day 0 until 9 weeks after administration of the last dose of study drug.

### **6.3 STUDY ASSESSMENTS**

Please refer to [Table 3](#) and [Section 6](#) (Study Procedures) for an overview of the study procedures and schedule of events. Data will be collected via an eCRF for each randomized patient.

All patients will provide written informed consent before any study-specific assessment is performed. A study-specific assessment is defined as a procedure that is not part of the routine assessments performed for diagnostic purposes or standard care. Screening assessments should occur within 6 weeks prior to administration of the study treatment (ie, on Days -42 to -1). The immunization status should be confirmed at least 14 days prior to the planned administration of study drug (ie, on or before Day -14).

#### **6.3.1 Demographic data**

The date of birth, sex, race, and ethnicity will be documented, as permitted by local regulations.

#### **6.3.2 Medical history**

A detailed general medical history of clinically significant diseases and surgeries will be collected during Screening. Additionally, a detailed medical history of the patient's primary CAgD as well as history of all blood transfusions will be reviewed and recorded.

#### **6.3.3 Height, body weight, and vital signs**

Height, body weight, and vital signs will be documented. Vital sign measurements (including oral temperature, respiratory rate, supine blood pressure, and pulse rate) will be obtained at the time points specified in [Table 3](#). Vital signs will be measured after the patient has been supine for at least 5 minutes. Vital signs should be measured before any other procedures that may affect pulse rate or blood pressure (eg, blood draws).

#### **6.3.4 Electrocardiograms**

A 12-lead ECG will be obtained at the time points specified in [Table 3](#). Patients will be supine for at least 5 minutes prior to obtaining an ECG measurement. The ECG should be performed before any other procedures that may affect heart rate (eg, blood draws).

The Investigator's overall interpretation of the ECG will be recorded and any abnormalities reported.

### 6.3.5 Physical examinations

Full and brief physical examinations will be performed at the time points specified in [Table 3](#). The time and date of the physical examinations will be recorded in the source document and eCRF, and any clinically significant changes from baseline will be recorded as AEs.

Full physical examinations will consist of the following: general appearance, head and neck, eyes and ears, nose and throat, chest, lungs, heart, abdomen, extremities and joints, lymph nodes, skin, and neurology.

Brief physical examinations will consist of the following: general appearance, chest, lungs, heart, abdomen, and skin.

### 6.3.6 Immunization review

The patient's medical and vaccination history will be reviewed to ensure that each patient is up-to-date with all required immunizations; if not already vaccinated against *Neisseria meningitidis*, including serogroup B *meningococcus*, where available, *Haemophilus influenzae*, and *Streptococcus pneumoniae* within 5 years of enrollment, these will be administered following informed consent, as applicable, per [Table 3](#) and as described in [Section 6.1.1.1](#) (Screening procedures) or [Appendix I](#) for Japan.

### 6.3.7 Clinical laboratory evaluations

Clinical laboratory evaluations (including hematology panel, clinical chemistry panel, iron panel, erythropoietin assay, coagulation safety panel, SLE panel, virology/serology panel, disease-related biomarkers, and urinalysis) as outlined in [Appendix A](#) will be performed at the time points specified in [Table 3](#). Clinical laboratory results will be reviewed by the Investigator and results outside of the reference ranges will be documented and clinical significance noted.

Local laboratory values may be utilized for eligibility evaluation and medical management of the patient, including assessing the hemoglobin criteria necessitating blood transfusions. Detailed information on the allocation of samples for central or local laboratory processing will be available in the Laboratory Manual.

### 6.3.8 Additional testing in case of hypersensitivity/allergic reaction

If a patient exhibits signs of a hypersensitivity/allergic reaction during study drug administration, the study drug infusion should be stopped immediately, and medical treatment provided, as appropriate.

If a suspected anaphylactic reaction occurs ([18](#)), the following labs may be obtained per the discretion of the Investigator, after discussion with the Sponsor Medical Monitor:

- Approximately 30 to 120 minutes after the start of symptoms: blood draw for ADAs (including isotyping), tryptase, IL-6, IL-33, plasma histamine, CICs, and complement levels (CH50). A follow-up tryptase level should be obtained 8 days following the reaction.

- 24-hour urine collection for methylhistamine analysis (ideally collection should be started within 6 hours of onset of symptoms and collected even if the patient is sent to the emergency room; patient can be provided with a container for the collection).

## **6.4 PHARMACOKINETIC PROCEDURES**

### **6.4.1 Pharmacokinetic blood sample collection and processing**

Blood samples for PK analysis of BIVV009 levels and ADAs against BIVV009 will be collected via an indwelling catheter and/or via direct venipuncture from the arm opposite from the site of infusion. Blood samples will be collected at the time points specified in [Table 3](#). If an indwelling catheter is used, saline flushes will be used.

### **6.4.2 Analytical methodology**

Plasma concentrations of BIVV009 will be determined using a validated analytical procedure. Specifics of the analytical methods will be provided in a separate document.

## **6.5 PHARMACODYNAMIC PROCEDURES**

### **6.5.1 Pharmacodynamic and ADA blood sample collection and processing**

Blood samples for ADA and PD analysis of the Complement System Classical Pathway levels (Wieslab assay) will be obtained via an indwelling catheter and/or via direct venipuncture. Blood samples for PD analysis will be collected at the time points specified in [Table 3](#). Complement assays will also be performed on samples, including:

- Total complement (CH50)
- Total C4
- C1q
- C1s

If an indwelling catheter is used, saline flushes will be used.

### **6.5.2 Analytical methodology**

PK, PD, and ADA parameters will be determined using a validated analytical procedure. Specifics of the analytical methods and appropriate matrices for the different parameters will be provided in a separate document.

## **6.6 SAFETY PROCEDURES**

Safety evaluations as needed for medical management of the patient may be repeated at the Investigator's (or designee's) discretion.

Every effort will be made to schedule and perform the procedures in accordance with the nominal time, giving considerations to appropriate posture conditions, practical restrictions, and the other procedures to be performed at the same time point.

The order of priority for scheduling procedures around a time point is (in descending order of priority):

- PK and PD blood sampling
- ADAs against BIVV009
- Vital sign measurements
- ECGs
- Blood and urine samples for clinical laboratory testing
- Physical examinations

## **6.7 ADVERSE EVENTS AND LABORATORY ABNORMALITIES**

It is the responsibility of the Investigator to report all AEs in the eCRF. The AE and SAE reporting period will begin from the time the patient signs the ICF and continue through 9 weeks after administration of the last dose of study drug. Any SAE must be reported within 24 hours of the knowledge of the occurrence to the Study Medical Monitor and the designated Clinical Research Organization's (CRO) Clinical Safety Group. Refer to [Section 6.7.4](#) for further details regarding SAE reporting procedures.

For urgent medical issues in which the study's Medical Director should be contacted, please refer to the study reference manual's Official Study Contact List for complete contact information.

### **6.7.1 Definition of adverse events**

An AE is defined in the International Council for Harmonisation (ICH) Guideline for Good Clinical Practice (GCP) as "any untoward medical occurrence in a patient or clinical investigation subject administered a pharmaceutical product and which does not necessarily have a causal relationship with this treatment" (ICH E6: Section 1.2). An AE can therefore be any unfavorable and unintended sign (including an abnormal laboratory finding, for example), symptom, or disease temporally associated with the use of a medicinal (investigational) product, whether or not considered related to the medicinal (investigational) product.

#### **6.7.1.1 Definition of adverse drug reactions**

Adverse drug reactions are defined as all noxious and unintended responses to a medicinal product related to any dose administered. The phrase "responses to a medicinal product" means that a causal relationship between a medicinal product and an AE is at least a reasonable possibility (ie, the relationship cannot be ruled out).

The following categories for determining the causal relationship to the investigational medicinal product are to be used:

**Probable (must have first three):**

- It follows a reasonable temporal sequence from administration of study drug.
- It cannot be reasonably explained by the known characteristics of the patient's clinical state, environmental or toxic factors, or other modes of therapy administered to the patient.
- It disappears or decreases on cessation or reduction in dose.
- It follows a known pattern of response to the suspected drug.
- It reappears upon re-challenge.

**Possible (must have first two):**

- It does not follow a reasonable temporal sequence from administration of the drug.
- It may readily have been produced by the patient's clinical state, environmental or toxic factors, or other modes of therapy administered to the patient.
- It does not reappear or worsen when the drug is re-administered.

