**Unrelated:**

An AE will be considered "Unrelated" to the use of the investigational drug if there is not a reasonable possibility that the event has been caused by the product under investigation and does not meet the criteria for drug relationship listed under possible or probable. Factors pointing toward this assessment include, but are not limited to, the lack of reasonable temporal relationship between administration of the drug and the event, the presence of a biologically implausible relationship between the product and the AE (eg, the event occurred before administration of drug), or the presence of a more likely alternative explanation for the AE.

In case of missing causality assessment in the eCRF or SAE reporting form, the event will be regarded as possibly related unless further specified. Any SAE recorded as probably or possibly related will be categorized as "related" for regulatory reporting purposes.

A serious drug reaction is an adverse drug reaction that meets the definition of a serious event (provided below).

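### Protocol 6.7.1.1 defines Possible causality by features it also lists as pointing to Unrelated, so some events are forced into the related group and others have no fitting category

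*Protocol*

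**What the plan says.** Protocol 6.7.1.1 opens with a standard. An adverse drug reaction is one where causality is "at least a reasonable possibility (ie, the relationship cannot be ruled out"). It then gives three categories for investigators to use.

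- **Probable** needs the first three of its five items: plausible timing, no reasonable explanation from the patient's condition, surroundings or other treatment, and improvement when the drug is stopped or reduced.
- **Possible** needs the first two of its three items. The first is "It does not follow a reasonable temporal sequence from administration of the drug". The second is that other causes could readily have produced the event. The third, optional, is a negative re-challenge.
- **Unrelated** applies when there is no reasonable possibility of a drug cause and the event "does not meet the criteria for drug relationship listed under possible or probable". The factors given for it are "the lack of reasonable temporal relationship between administration of the drug and the event", biological implausibility ("eg, the event occurred before administration of drug"), and a likelier alternative explanation.

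The same section adds that with no causality entry "the event will be regarded as possibly related unless further specified". It also says: "Any SAE recorded as probably or possibly related will be categorized as" related for regulatory reporting. Section 4.7.2 of the Part A SAP and of the Part B SAP both pool Possible with Probable as Related and count missing relationship as Related. Neither SAP restates or corrects the Possible list.

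**The concern.** Two features, poor timing and a ready alternative cause, are required for a category that counts as related. The same section offers those features as grounds for Unrelated. Because Unrelated is closed to any event meeting the Possible list, the text does not let the investigator resolve the conflict in favour of Unrelated.

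The reverse problem also arises. Good timing disqualifies an event from Possible. If it also falls short of Probable, no related category fits it, although the opening standard may be met.

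This does not look like one stray negative. All three items under Possible point away from the drug.

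What is at stake is the relatedness label: the regulatory status of serious events under 6.7.1.1, and the related-TEAE and related-SAE tables in both parts. Part B has long-term safety as its primary objective and no concurrent control, so its related-event tables have to be read on their own.

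**Working it through.** No figure in the plan depends on this text, so there is nothing to reproduce. The check is one of logic.

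**Inputs**, all from Protocol 6.7.1.1, as three yes/no attributes:
- T: plausible timing
- A: a ready alternative cause
- D: improvement on stopping or reducing the drug

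**Rules**
- Probable = T and not-A and D
- Possible = not-T and A
- Unrelated is open only if there is no reasonable possibility of a drug cause and neither rule above is met

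**All 2 × 2 × 2 = 8 combinations**

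| T | A | D | List met |
|---|---|---|---|
| yes | no | yes | Probable |
| yes | no | no | neither |
| yes | yes | yes | neither |
| yes | yes | no | neither |
| no | yes | yes | Possible |
| no | yes | no | Possible |
| no | no | yes | neither |
| no | no | no | neither |

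Totals: Probable 1, Possible 2, neither 5 (3 with plausible timing, 2 without).

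**First consequence.** Both Possible rows have implausible timing and an alternative cause. Unrelated is barred for them even when the investigator sees no reasonable possibility of a drug cause.

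**Second consequence.** The 3 plausibly timed rows marked neither can be Unrelated only if there is no reasonable possibility. If the relationship cannot be ruled out, no category fits.

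**How much comes from the negated item.** Reverse it, so that Possible = T and A. Two of the 3 plausibly timed gaps then become Possible. One remains: plausible timing, no alternative cause, no improvement on stopping. That gap comes from the dechallenge requirement in Probable, and reversing the timing item alone would not close it.

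**Assumption.** A treats the alternative-cause items in Probable and Possible as exact opposites. If an intermediate state is allowed (an explanation exists but is not a ready one), it fails both lists. The count becomes 2 × 3 × 2 = 12: Probable 1, Possible 2, neither 9. The conflict remains and the gap widens.

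**The case against.** **Investigators will use the ordinary meaning of possible, and the Unrelated items are only factors.** This is fair, and it is why the effect on actual coding cannot be sized. But the Possible items are stated as mandatory, and the bar on Unrelated is part of its definition. Common sense here means departing from the text, and sites may depart differently.

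**The opening standard says nothing about timing.** Correct. A reader might infer that the Possible list flatly contradicts it. The direct conflict is with the Unrelated paragraph. The departure from the opening standard is an inference, drawn from events that cannot be ruled out yet have no category.

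**The text over-counts related events.** A reader might infer this from the forced Possible rows, or infer under-counting from the plausibly timed rows with no category. The documents settle neither. Missing causality defaults to related, and Unrelated is not open while a reasonable possibility remains, but a more likely alternative explanation is also a listed pointer to Unrelated.

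**Pre-dose events show the size.** Recording starts early ("The AE and SAE reporting period will begin from the time the patient signs the ICF"), and screening runs from Day -42 to Day -1: 42 days, or 42 + 7 = 49 with the extension in Table 3 footnote a. A reader might take that window as a measure of misclassification. It is not. It counts days, not events, and the Unrelated paragraph names pre-dose onset as an example. Both SAPs limit summary tables to treatment-emergent events, so pre-dose events should not reach the related-event tables, assuming treatment-emergent means onset after first dose.

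**The rule is the same in both arms.** True, and Part A is double-blind. Nothing in the text favours an arm.

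**Conclusion.** The contradiction is real, sits in current mandatory text, and is corrected nowhere in the protocol or either SAP. As written, an implausibly timed event with a ready alternative cause is classed as related, and a plausibly timed event short of Probable has no related category. It should be fixed, although its reach is limited.

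The number of events affected and the net direction cannot be derived. For scale only: with 20 patients per group (Protocol 7.10), one patient moving into or out of the related group shifts that group's percentage by 1/20 = 5 points. That is a unit of sensitivity, not an estimate.

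Safety analyses in both SAPs are descriptive, with no testing. Efficacy, overall TEAE and SAE incidence, and the 24-hour reporting of serious events during the study do not depend on the label.

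The conclusion rests on reading the mandatory items literally. The 8-way count also assumes that the two alternative-cause items are opposites.

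**What to change.** Reconcile the standard and the three categories in Protocol 6.7.1.1:

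- Remove the negated timing item as a requirement for Possible.
- Define Possible as any event whose relationship to the drug cannot be ruled out and that does not meet Probable. An alternative cause is allowed but not required. This also closes the separate dechallenge gap.
- Keep lack of temporal relationship only as a factor under Unrelated.

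Issue a clarification to sites with the new wording.

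Any re-confirmation of recorded causality should be done by investigators before the relevant database lock (Protocol 7.9), and blinded for Part A. The sponsor should set its scope. The attributes listed in Protocol 6.7.2 include neither alternative cause nor dechallenge result, so the affected events cannot readily be selected from the data, and a narrow query cannot be assumed.

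The cost is a small amendment, a site communication and some query work. Some relatedness values may change. No other data and no efficacy analysis would.

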**Unrelated:**

An AE will be considered "Unrelated" to the use of the investigational drug if there is not a reasonable possibility that the event has been caused by the product under investigation and does not meet the criteria for drug relationship listed under possible or probable. Factors pointing toward this assessment include, but are not limited to, the lack of reasonable temporal relationship between administration of the drug and the event, the presence of a biologically implausible relationship between the product and the AE (eg, the event occurred before administration of drug), or the presence of a more likely alternative explanation for the AE.

In case of missing causality assessment in the eCRF or SAE reporting form, the event will be regarded as possibly related unless further specified. Any SAE recorded as probably or possibly related will be categorized as "related" for regulatory reporting purposes.

A serious drug reaction is an adverse drug reaction that meets the definition of a serious event (provided below).

**6.7.1.2 Definition of serious adverse events**

An SAE is defined as any untoward medical occurrence (AE) that at any dose:

- Results in death
- Is life-threatening (patient was at immediate risk of death at the time of the event)
- Requires inpatient hospitalization or prolongation of existing hospitalization
- Results in persistent or significant disability/incapacity
- Is a congenital anomaly/birth defect
- Any other significant medical condition

A hospitalization meeting the regulatory definition for “serious” is any inpatient hospital admission. Any AE that does not meet one of the definitions of serious (ie, important medical events that may not be immediately life-threatening or result in death or hospitalization but may jeopardize the patient or may require interventions to prevent one of the other outcomes listed above [eg, emergency room visit, outpatient surgery, or requires urgent investigation]) may be considered by the Investigator to meet the “other significant medical condition” criterion for classification as an SAE. Examples include allergic bronchospasm, convulsions, and blood dyscrasias.

If a subject develops a Grade 3 or higher allergic reaction per Common Terminology Criteria for Adverse Events (CTCAE) grading or an anaphylactic reaction (see [Section 6.3.8](#)) in association with BIVV009 administration, the event should be reported as an SAE.

